8.7.3. Rate of Expert-Confirmed HAE Events during Dosing in the Effective Dosing Period

The rate of expert-confirmed HAE events during dosing in the effective dosing period is a secondary endpoint for Part 1.

Summaries and analysis of the expert-confirmed event rate using the ITT population for the effective dosing period (Day 8 through Week 24, inclusive) will be conducted using negative binomial regression, similar to what is done for the primary efficacy endpoint analysis.

Summary displays will be updated at the end of Part 2 to include data collected during Part 2 of the study. For subjects originally randomized to placebo, data on active treatment will be summarized using the adjusted visits.

8.7.4. Use of HAE Event Medications

The use of HAE event medications over 24 weeks is an exploratory efficacy endpoint for Part 1 and a secondary endpoint for Part 2. Use of HAE medications based on diary data will be summarized separately from concomitant medications. In addition, summaries and analyses of the rate of expert-confirmed HAE events requiring treatment will be provided for Part 1 and for the entire study period. The analysis will be performed similarly to the analysis of rate of confirmed HAE events. For a list of medications that qualify as HAE event medications, see Section 6.7.5.7. Separate summaries of HAE event medication use for Part 3 will be produced based on adjusted subject-reported attacks.

A Kaplan-Meier (KM) plot of time to first use of targeted HAE rescue medication to treat an expert-confirmed event and corresponding summary table will be produced for Part 1.

The rate of the use of any HAE medications (ie medication rate) used to treat expert-confirmed events will be calculated as doses taken for expert-confirmed events per month (28 days), similar to the calculation of the event rate. This will be analyzed using a negative binomial regression analysis in the same manner as the primary endpoint, with the number of rescue medication doses included as the dependent variable, treatment included as a fixed effect, baseline expert-confirmed event rate included as a covariate, and the logarithm of duration on treatment included as an offset variable. This analysis will also be conducted for the medication rate for subject-reported events.

A summary of expert-confirmed events requiring treatment with targeted HAE medications that will display the first medication taken and number of uses of any other targeted medications for each attack will be presented.

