5.4.4. Rationale for Control Group and Prohibition of Current Prophylactic Medications

In the current study, all participants must have access to an effective, approved treatment for attacks or episodes of angioedema as part of their routine medical care. Each subject will continue to use his or her prescribed acute medication to treat attacks, under the medical

management plan advised by his or her physician, throughout the study. This is consistent with guidance documents that strongly support the position that all subjects with C1-INH deficiency should have access to medications for treating attacks (Cicardi, Bork et al. 2012, Zuraw, Banerji et al. 2013).

While in some countries (not including Japan) there are approved therapies for prophylaxis against HAE attacks, such as C1-INH, consensus recommendations do not exist for either prophylactic treatment as a standard of care or a definition of indications for prophylaxis.

The International World Allergy Organization/European Academy of Allergy and Clinical Immunology guidelines for the management of HAE recommends prophylaxis be considered for patients who “face events in life that are associated with increased disease activity,” specifically C1-INH for first-line, long-term prophylaxis (Maurer, Magerl et al. 2018). Given the lack of wide availability of such a treatment in Japan and the limitations of intravenous (IV) therapy, a study of an orally available product such as BCX7353 is appropriate.

A subject randomized to placebo in the current study who has access to effective attack medications is therefore considered to be treated in line with current guidelines.

Unapproved prophylactic therapies may be used by some HAE patients in Japan. To guard against enrolling subjects who need prophylaxis, subjects must meet an inclusion criterion assessing whether they are medically appropriate for on-demand treatment as the sole medicinal management for their HAE during the study. The informed consent and assent for this study will inform subjects on available prophylactic therapies and will note that they cannot discontinue prophylaxis for the sole purpose of screening for the trial; there must be medical and personal choice reasons to do so. If a subject has voluntarily discontinued prophylactic therapy outside of the specified window (see below) in advance of the Screening visit for medical or personal choice reasons, then they may be screened for study eligibility.

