- The angioedema events must have either been treated, required medical attention, or have been documented to cause functional impairment, based on the subject's entry in the electronic diary (e-diary). Functional impairment is defined as the subject not being able to perform his or her daily activities without restriction (ie, subject records that he/she is at least slightly restricted in daily activities during an angioedema event).
- The angioedema events must include symptoms of swelling. The expert will consider that symptoms of swelling, in addition to visible swelling, may also include symptoms in the oropharyngeal or abdominal regions that are indicative of internal swelling.
- The angioedema events are otherwise confirmed by an independent expert to be angioedema events.

A study schematic can be found in [Figure 1](#).

Throughout the entire study, details of all angioedema events (attacks, symptoms, or swelling due to HAE) and compliance with study drug will be recorded in an e-diary. Angioedema events will be treated in accordance with the subject's normal standard of care. Within approximately 2 business days of the end of each angioedema event that occurs from the screening visit through the Week 52 visit in Part 2, subjects will be contacted by the investigator (or appropriately trained designee) to discuss the clinical characteristics of the angioedema event, any questions on the entered data, or to gain additional details on the event that are not included in the e-diary that the investigator deems important to clinically evaluate the event, as applicable. The investigator-collected information, in conjunction with the e-diary record, will be used by an independent expert to verify or reject each angioedema event recorded in the e-diary as a confirmed angioedema event. All expert-confirmed angioedema events must include symptoms of swelling; prodromal symptoms in the absence of swelling are not considered angioedema events, regardless of treatment. The expert will consider that symptoms of swelling, in addition to visible swelling, may also include symptoms in the oropharyngeal or abdominal regions that are indicative of internal swelling. Under no circumstances should the run-in angioedema event requirement for eligibility be disclosed to study subjects.

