11.4. Angioedema Events and Dosing e-Diary, Investigator Event Follow-up and Confirmation

The sponsor will supply e-diaries to sites. Study-specific manuals will be prepared for both site staff and subjects for use of the e-diary for this study.

While a subject has an e-diary in his or her possession, the subject will fill out the angioedema event e-diary daily, recalling whether or not symptoms of an angioedema event were experienced in the previous 24 hours. Subjects will fill out the e-diary regardless of the presence of HAE symptoms. If the subject does report an angioedema event, additional details about the angioedema event will be entered into the e-diary including start and stop time of the angioedema event, angioedema event symptoms, anatomical location of swelling (if applicable), severity, treatment(s) administered and times of administration, and whether additional medical care was sought for the angioedema event. During study drug administration in Parts 1 and 2, subjects will also record the times of day study drug was taken in the e-diary on a daily basis.

All subjects will fill out an HAE e-diary during the run-in period of 56 consecutive days from the screening visit to enable the qualifying angioedema event rate to be established. Subjects will continue to fill out their e-diary after the run-in period in advance of the baseline visit. Subjects will continue to fill out the e-diary daily during the treatment and follow-up periods.

Site staff will set up the e-diary when a subject is initially provided an e-diary at the screening visit and then as needed during the study (eg, to end Part 1/begin Part 2 or to end Part 2/begin Part 3). Subjects should be instructed to bring their e-diary with them to each study visit, up to and including Week 104, except Weeks 2 and 26. Once a subject completes or discontinues the study, the site should ensure that e-diaries are returned.

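### SAP 8.7.4 adjusts on-demand medication use for baseline event rate but not for the subject's own run-in dose rate, which may cost some precision in the combined analysis

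*SAP*

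**What the plan says.** SAP 8.7.4 defines a medication rate (doses taken for expert-confirmed events, per 28 days) and models it like the primary endpoint: a negative binomial regression with "number of rescue medication doses included as the dependent variable, treatment included as a fixed effect, baseline expert-confirmed event rate included as a covariate" and log duration on treatment as the offset. The same model is repeated for subject-reported events. Events requiring treatment are analysed in the same way as the event rate. On status, the SAP states: "The use of HAE event medications over 24 weeks is an exploratory efficacy endpoint for Part 1 and a secondary endpoint for Part 2".

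The covariate comes from SAP 6.6.1. It counts qualifying events from screening to first dose, scaled to 28 days. It does not count doses. Under SAP 4.4.1 an event can qualify without having been treated, because functional impairment is enough.

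The missing information is collected in Study 301. Protocol 11.4 has the diary capture "severity, treatment(s) administered and times of administration, and whether additional medical care was sought for the angioedema event", and states: "All subjects will fill out an HAE e-diary during the run-in period of 56 consecutive days from the screening visit". Treatment of events is not standardised. Protocol 7 says: "Angioedema events will be treated in accordance with the subject's normal standard of care". Protocol 5.4.4 says: "Each subject will continue to use his or her prescribed acute medication to treat attacks".

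No run-in dose rate is derived in SAP 6.6, listed for baseline summary in SAP 7.9, or used in any model. By contrast, the models for AE-QoL (SAP 8.7.1), EQ-5D-5L (9.1), TSQM (9.2) and WPAI (9.3) each include a baseline event term and the baseline value of the outcome itself.

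**The concern.** The number of doses depends on two things: how often a subject has events, and what that subject does about them. The model adjusts for the first only. Two subjects with the same baseline event rate can differ in dose rate from the start if one treats every event and the other treats few. If that habit carries over from run-in to Part 1, the difference goes into the dispersion parameter and widens the interval for the rate ratio. A chance imbalance between arms in habitual treaters would also go uncorrected. The variable that would absorb this is already recorded in Study 301. What is at stake is precision and chance imbalance.

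**Working it through.** **1. The plan's own figure.** The documents state no power or precision for the medication endpoint. The nearest figure is 61% power for the primary endpoint in Study 301 alone (SAP 4.3.1). With 8 per group, difference 0.6 and SD 0.5, the noncentrality is 0.6 / (0.5 × √(2/8)) = 2.4. A two-sided 5% t-test on 14 df then has 60.8% power. The figure reproduces, and this point does not affect it.

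**2. What has to be assumed.** The documents do not say how much doses per event vary between subjects, or how stable that is. Two simulation models cover the range. Both fit the SAP model with and without a run-in dose-rate term. The combined analysis is taken as 48 per arm (SAP 4.3.2).

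**3. Treat-or-not model.** Each subject treats a fixed share of events, drawn from a Beta distribution with SD √(ab / ((a+b)²(a+b+1))). Each treated event takes one dose plus Poisson(0.3) extra doses. The rate reductions are 46% and 54%, as for rescue use in Study 302 (Protocol 5.3.1). Results at 48 per arm:

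| Share treated | Mean, SD of share | Fall in empirical SD of log rate ratio |
|---|---|---|
| Beta(8, 2), nearly all treat | 0.80, 0.12 | 0-1% |
| Beta(3, 2), moderate | 0.60, 0.20 | about 3% |
| Beta(1.2, 0.8), wide | 0.60, 0.28 | about 7-9% |

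One wide-variation run went from 0.208 to 0.195 (6%). Its model SE fell from 0.199 to 0.177 (11%), so model SEs overstate the gain. A 3% fall in SD is worth 1/0.97² = 1.06 times the subjects, and an 8% fall is worth 1/0.92² = 1.18 times.

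**4. Doses-per-event model.** Doses per event vary log-normally between subjects. Assumed: 2.6 events per 28 days, squared CV 0.4, at least 2 events in a 56-day run-in, and 1.2 doses per event. The event rate ratios are 0.70 and 0.56, from Protocol 5.3.1. Cells show the empirical SD of the log rate ratio (150 mg vs placebo) without → with the term.

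| Habit SD (log) | Run-in to Part 1 correlation | 48 per arm | 8 per arm |
|---|---|---|---|
| 0 | – | 0.137 → 0.136 | 0.377 → 0.389 |
| 0.3 | 1.0 | 0.155 → 0.147 | 0.392 → 0.392 |
| 0.6 | 1.0 | 0.197 → 0.170 | 0.524 → 0.454 |
| 0.6 | 0.8 | 0.217 → 0.183 | 0.517 → 0.480 |
| 0.6 | 0.5 | 0.213 → 0.201 | 0.526 → 0.518 |
| 0.9 | 1.0 | 0.300 → 0.202 | 0.735 → 0.545 |

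At 48 per arm the fall runs from 1% (0.136/0.137) to 33% (0.202/0.300). At 8 per arm it runs from a 3% rise to a 26% fall. At correlation 0.5 a smaller run with 8 per arm gave a 2% rise. The 48-per-arm cells rest on 200 to 300 trials each, so differences of a few points are noise. A term in log(rate + 0.25) gave similar ratios at 48 per arm (for example 0.858 against 0.863 at habit SD 0.6, correlation 1).

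**5. Plausibility check against Study 302.** Protocol 5.3.1 reports a 46.3% reduction in rescue use at 110 mg with p < 0.001. If this came from a log-link model (the protocol does not say), log(0.537) = -0.622 and the SE was below 0.622/3.29 = 0.189 at about 40 per arm. That is about 0.189 × √(40/48) = 0.173 at 48 per arm. The wide case in step 3 has SE 0.199. In step 4 the model SE without the term, for the 150 mg contrast, is 0.152, 0.183 and 0.224 at habit SD 0.3, 0.6 and 0.9. The largest gains therefore belong to settings noisier than Study 302 appears to have been.

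**6. False positives at 8 per arm.** The model SE is already too small there: 0.416 against an empirical 0.524 at habit SD 0.6. Under the null in the treat-or-not model (1,500 trials, nominal 5% Wald test), rejection without and with the term was 10.1% and 12.9% (wide), 10.5% and 11.3% (moderate), and 11.0% and 11.6% (nearly all treat). A second set of runs gave about 9% and 13% for the wide case. The empirical SD fell only about 4-7% there. At 48 per arm, null rejection was similar with and without the term.

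**The case against.** The strongest reply is that little depends on this. The endpoint is exploratory in Part 1 and outside the four-endpoint hierarchy of SAP 8.5, and Part 2 is descriptive (SAP 8.1). Both doses already reached p < 0.001 on rescue use in Study 302 alone, so the combined analysis is not short of precision. Every subject must have access to an approved acute treatment and be able to use it (Protocol 8.2.1). If nearly everyone treats, the gain is about nil. The SAP is also consistent with its own practice on days with symptoms (8.7.2), which adjusts for baseline event rate only. Tables 14.1.3.5 and 14.1.3.6 already show baseline acute-treatment information by arm. Finally, nothing provided shows that Study 302 recorded run-in doses in the same way.

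All of this stands as a limit on importance. It does not remove the omission. Those tables describe treatments used and are not a run-in dose rate, and four other models in the same SAP do adjust for the outcome's own baseline.

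A reader might infer that the loss is greatest in Study 301 because it is small, and might point to simulated power for 150 mg rising from 40% to 50% with 8 per arm. That does not hold. The gain is generally equal or larger at 48 per arm, and with 8 per arm part of the apparent power is extra false positives.

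**Conclusion.** The point holds as a minor improvement to the combined 301 and 302 analysis. The SAP leaves out a baseline value of the outcome that Study 301 collects, and baseline event rate is an incomplete stand-in because events can count untreated and subjects treat by their own practice. With 48 per arm the empirical SD of the log rate ratio would fall by about 0-1% if nearly all treat and about 7-9% with wide variation in the share treated. It would fall by more if doses per event vary widely and persist, although step 5 suggests that the extreme settings are unlikely. These sizes rest on assumed habits.

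A reader might also infer bias in the treatment effect, or a threat to a confirmatory claim. The documents support neither: allocation is randomised, and no hierarchical test uses this endpoint. In Study 301 alone no gain in power should be claimed.

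**What to change.** - **Derive** run-in doses per 28 days over the same window as the baseline event rate (screening to first dose). Match it to the outcome: doses for expert-confirmed events in one model, for subject-reported events in the other.
- **Combined analysis:** if Study 302 recorded run-in doses comparably, add log(rate + 0.5) next to baseline event rate in both medication-rate models. Use the baseline treated-event rate likewise in the model for events requiring treatment. If Study 302 did not, keep the current model and say so.
- **Study 301 alone:** keep the current model, report the adjusted one only as a sensitivity analysis, and summarise run-in dose rate by arm so that any imbalance is visible.
- **Timing:** specify this before Part 1 unblinding; otherwise label it a sensitivity analysis. Study 302 Part 1 results are already known, so fix the exact form of the term before refitting those data.

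The cost is one derived variable, one model parameter and one summary row. With 8 per arm the extra term can raise a Wald false-positive rate that is already inflated, which is why it should not replace the current model there.

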8.7.5. Discontinuations due to Lack of Efficacy

Discontinuation due to lack of efficacy is a secondary endpoint for Part 2.

A summary of the number of subjects who discontinue due to lack of efficacy will be provided with subject disposition. The summary will include the number and percent of subjects who discontinue due to lack of efficacy during Part 1 and Part 2 as well as overall.

8.8. Analysis of Additional Exploratory Efficacy Endpoints

8.8.1. Number and Proportion of Subjects with No Events

The number and proportion of subjects with no events over 24 weeks is an exploratory endpoint for Part 1. This information will be descriptively summarized. The summary will be repeated at the end of Part 2 as a summary of the number and proportion of subjects with no events over the entire dosing period of 52 weeks for those originally randomized to active treatment. A summary of 24-Week data at the end of Part 2 will be conducted including subjects originally randomized to placebo. The summary will show the number and proportion of subjects with no events during the first 24 weeks of active treatment, whether received in Part 1 or Part 2 and separately for those who started active treatment in Part 2. Subjects who discontinue treatment prior to the end of the reporting period of interest will not be considered event-free. A separate summary of the number and proportion of subjects with no adjusted subject-reported events in Part 3 will be provided.

For Part 1, a chi-squared test will be used to test whether there is a difference in the proportion of subjects with no events comparing each active dose to placebo. For the chi-squared analysis, if the expected number of subjects in any individual cell is < 5 , Fisher's exact test will be used instead the chi-squared test.

A KM plot and corresponding summary of time to first event will be produced for Part 1 for both the entire dosing period and the effective dosing period (Day 8 to Week 24).

8.8.2. Proportion of Responders to Study Drug.

Subjects will be classified as responders or non-responders for Part 1 as discussed in Section 6.7.5.4. A responder is defined as a subject who has at least a 50% relative reduction in the rate of expert-confirmed HAE events meeting the stricter screening criteria during treatment compared with the baseline event rate. A summary of the number and proportion of responders by study treatment will be produced. Logistic regression with responder status as the outcome variable and treatment and baseline event rate as independent variables in the model will be used to compare each active treatment to placebo treatment. Point estimates of the odds ratios for response comparing 110 mg to placebo and 150 mg to placebo will be calculated along with corresponding 95% CIs. If the proportion of responders is near zero for the placebo treatment (or for either active treatment), logistic regression may not be an appropriate methodology for analysis and Fisher's exact test will be used in place of logistic regression. This analysis will also be conducted for responders with at least 70% and 90% relative reduction and conducted by subgroups for 50%, 70%, and 90% relative reduction. Forest plots will be produced to accompany the subgroup analyses.

A waterfall plot of relative reduction by treatment will be produced. For the combined study, this plot will include differentiation in the bar fill for Japan and the rest of the world.

A listing of expert-confirmed events that are not included in any adjusted expert-confirmed events will be provided.

The relationship of selected baseline characteristics with the proportion of responders with at least 50% and 70% relative reduction, respectively, will be explored using an appropriate model-building method for Part 1.

8.8.3. Event Characteristics

Characteristics of events including location of event (see Section 6.7.5.9), laryngeal events (see Section 6.7.5.10), duration of events from start to finish and from start to the time the worst symptoms of the event were over, time since last dose, triggers, swelling, other symptoms, whether the event was treated, severity as assessed by the patient and by the investigator, ability to do daily activities, appearance affected, professional care sought, and location of professional care will be summarized and listed.

A summary of duration of event for abdominal, peripheral, and mixed events will also be provided (see Table 11).

8.9. Summary of Reasons for Efficacy Non-Evaluability/Exclusion from Efficacy Analyses

A listing of subjects excluded from the PP population will be provided along with reason for exclusion.

9. HEALTH OUTCOMES

9.1. EQ-5D-5L

EQ-5D-5L is a health outcomes endpoint for Part 1 and a secondary endpoint for Part 2. The 5-digit numbers representing the health state of each subject will be listed along with the VAS score and computed index value (Section 6.7.6.1). The VAS score and computed EQ-5D-5L index value will be summarized descriptively for Part 1 and for the entire study period.

Note that this study uses the questionnaire in its validated form for subjects to report their health status “*today*”. If the subject has had an HAE event since the last visit, starting at Week 4, the subject completes the questionnaire a second time to reflect back on health status during a “*usual event*”. On summary tables, the “*today*” and “*usual event*” questionnaire results will appear in different rows and analyses should be separated.

For Part 1, MMRM will be used to compare each active dose to placebo for each time point. For this analysis, either the CFB VAS score or EQ-5D-5L index value using the “*today*” questionnaire will be included as the dependent variable in the model with fixed effects for treatment, baseline event value, baseline VAS or EQ-5D-5L index score as appropriate, visit, visit by treatment interaction, and a random effect for subject included as independent variables. An unstructured covariance structure will be used.

Analyses at the end of Part 2 will be descriptive and will cover the entire study period.

For Part 1 and entire study period analyses, categorical summaries by treatment group and visit will be provided for responses to each individual question. In addition, summaries of VAS and index scores during a “*usual event*” will be provided.

Plots of VAS and EQ-5D-5L index mean scores over time and CFB mean scores will be provided for Part 1 analysis and at end of Part 2 analysis using the health status “*today*”. For Part 2, plots of mean scores over time by treatment will be shown separately for active treatment for the subjects originally randomized to placebo.

